## **5. STATISTICAL METHODS**

Descriptive statistical methods will be used to summarize the data from this study, with no hypothesis testing performed for the primary and other selected efficacy endpoints. Unless stated otherwise, the term “descriptive statistics” refers to number of subjects (N), number of observations (n), mean, median, standard deviation (SD), interquartile range, minimum, and maximum for continuous data and frequencies and percentages for categorical data.

Data required for an abbreviated clinical study report will be included in the data listings. Unless otherwise noted, the data will be sorted first by subject number, date, and time (as applicable).

The statistical analyses will be conducted with the SAS® System version 9.4 or higher.

### **5.1. SUBJECT DISPOSITION**

Subject disposition will be presented for the Safety Population in Tables and Listings. Summaries will include the reason(s) for discontinuation.

Subject disposition, protocol deviations and inclusion / exclusion criteria (for screened subjects) will be presented in data listings.

### **5.2. DEMOGRAPHIC CHARACTERISTICS**

Demographic characteristics will be summarized based on the Safety Population. Demographic variables including age, sex, ethnicity and race will be summarized. Age at the time of informed consent, as collected on the eCRF, will be summarized using descriptive statistics. Sex, ethnicity and race will be summarized with the number and percentage of subjects in each parameter category. Demographic characteristics will be presented in a data listing.

### **5.3. BASELINE CHARACTERISTICS AND CANCER HISTORY**

Baseline characteristics include weight (lb) and ECOG performance status score at baseline. Weight will be summarized using descriptive statistics. Frequency counts and percentages will be used to summarize subjects' ECOG performance status score and cancer history. Baseline characteristics and cancer history data will be presented in data listings.

### **5.4. MEDICAL HISTORY**

Medical history will be coded using Medical Dictionary for Regulatory Activities (MedDRA) version 23.0 or later by preferred term (PT) and system organ classification (SOC). The number and percentage of subjects experiencing each medical history event will be summarized by SOC and PT for the Safety Population. A listing of medical history will also be provided.

## **5.5. PRIOR THERAPIES AND SURGERY**

Prior systemic cancer treatment, prior radiation therapy, and prior cancer surgery will be listed. The following will be presented in summary tables:

- Number and % of subjects with any prior systemic cancer treatment
- Number and % of subjects with any prior radiation therapy
- Number and % of subjects with any prior cancer surgery

## **5.6. EXPOSURE AND COMPLIANCE**

Exposure and compliance to SPH4336 will be summarized and listed for the Safety Population. Duration of exposure (days), total (mg) and daily dose (mg) received and treatment compliance (%) will be summarized using descriptive statistics as described in Section 3.3.9.

Study drug administration, drug accountability, exposure, and compliance information will be presented in data listings.

## **5.7. EFFICACY ANALYSIS**

### **5.7.1. Primary Efficacy Endpoint**

The primary efficacy endpoint was to be the number and percentage of Efficacy-Evaluable subjects who had Progression-Free Survival (PFS) at 12 weeks. PFS is defined as the time interval from the date of the first dose of the SPH4336 until the first date at which disease progression is documented as assessed by the Investigator or date of death due to any cause, whichever occurs first. Subjects who were alive and progression-free at the time of data analysis were to be censored at the time of their last tumor assessment. Progression was evaluated by the investigator according to RECIST v1.1.

### **5.7.2. Primary Efficacy Analysis**

Limited efficacy analyses (tabulations) will be performed because this study ended prematurely due to futility (lack of efficacy). A by-patient listing of the objective responses evaluated by the investigators will be included in the report. The listing and table displaying duration of dosing will display the number of subjects who were dosed for 12 weeks or more without disease progression, and subjects who experienced disease progression at any time during the study, which were the criteria for inclusion in the Efficacy-Evaluable analysis dataset.

After 13 patients were enrolled in the study, too few Efficacy-Evaluable patients had reached 12 weeks of dosing without disease progression (2 of 10) to obtain a positive result for the primary study objective (see Section 3.1 Sample Size and Power). A futility analysis was performed, and it showed that the study would most likely not reach the threshold for a positive signal, even if additional patients were enrolled. A fourteenth patient was enrolled, but the study was closed (due to futility) before week 12.

Bayesian Evaluation of Futility

# Efficacy-Evaluable Patients	Stop Study if #Responses ≤
10	2
11	3
12	3
13	4
14	4
15	5
16	5
17	6
18	6
29	13

The analysis above was performed using available software (BOP2: Bayesian Optimal Phase II Design with Simple and Complex Endpoints (mdanderson.org)) and a simulation was conducted evaluating different sample sizes between current enrollment at the time of the evaluation (n=8) and full protocol enrollment (n=29).

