### ***10.4.3 Analysis Populations***

The Safety Population will include all subjects who receive at least one dose of SPH4336.

The PK-Evaluable Population will include all subjects who have had at least one pre- and post-dose PK assessment performed.

The Efficacy-Evaluable Population will include all subjects who receive at least 1 dose of SPH4336 and meet at least one of the following 2 criteria:

- Have at least 2 post-baseline disease assessments (for PFS at 12 weeks); or,
- Experience clinical progression.

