### **1.1. STUDY OVERVIEW**

This is a multicenter, non-randomized, open-label Phase 2 study of SPH4336 in subjects with well-differentiated/dedifferentiated or dedifferentiated liposarcomas.

SPH4336 was administered orally once each day in successive 28-day cycles until demonstration of progressive disease or the development of unacceptable toxicity.

The study incorporated a safety lead-in for the initial 10 subjects. Safety data was evaluated by the Safety Review Committee (SRC) after 10 subjects (minimum 1 cycle completed) were accrued and the SRC recommended that the study could continue.

Tumor assessments according to RECIST v1.1 were performed at baseline and every 6 weeks (from C1D1) for 36 weeks, then every 12 weeks thereafter.

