#### **4.2. EFFICACY-EVALUABLE POPULATION**

The protocol defined the Efficacy-Evaluable Population is to include all subjects who received at least 1 dose of SPH4336 and met at least one of the following 2 criteria: have at least 2 post-baseline disease assessments (including at Week 12) and received study treatment for at least 12 weeks without disease progression; or experience disease progression while on study treatment.

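### SAP 5.7.2 plans a dosing-based count but no table of the 12-week progression-free rate defined in SAP 5.7.1, and the evaluable set is worded inconsistently

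*SAP*

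**What the plan says.** **Endpoint.** SAP 5.7.1 gives the primary endpoint as the "number and percentage of Efficacy-Evaluable subjects who had Progression-Free Survival (PFS) at 12 weeks". The PFS event is investigator-documented progression or "date of death due to any cause, whichever occurs first".

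**What will be shown.** Under SAP 5.7.2, a duration-of-dosing listing and table will "display the number of subjects who were dosed for 12 weeks or more without disease progression", and also "subjects who experienced disease progression at any time during the study". The section calls these the inclusion criteria for the evaluable dataset. SAP Section 9 lists one efficacy table (14.2.1, Best Overall Response) and one dosing table (14.1.6, Safety Population). SAP 5.6, which governs exposure reporting, does not mention the count.

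**Evaluable set.** SAP 4.2 describes its definition as the protocol's. It asks for two post-baseline assessments, one of them at Week 12, and that the subject "received study treatment for at least 12 weeks without disease progression; or experience disease progression while on study treatment". Protocol 10.4.3 asks for at least one dose plus either of two criteria: "Have at least 2 post-baseline disease assessments (for PFS at 12 weeks"), or clinical progression. It sets no minimum time on treatment.

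**Declared changes.** SAP Section 7 says that no formal efficacy analysis and no biomarker analysis will be done, and that no other change is expected. It does not mention the evaluable set.

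**The concern.** Time on drug and time free of progression or death are different quantities. A dosing count cannot show a subject who stops drug early and is still progression-free at Week 12, nor a death without documented progression. Treatment continues "until demonstration of progressive disease or the development of unacceptable toxicity", so a subject who succeeds at Week 12 can progress later and fit both displayed groups.

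The report will state lack of efficacy. Its reader should be able to see the 12-week rate, its denominator and its uncertainty. As written, the reader has to rebuild the endpoint from listings and choose between two evaluable sets. Because SAP 4.2 presents its wording as the protocol's own, the change is also unlikely to be recorded as a departure from the protocol.

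**Working it through.** **1. Inputs.** Null rate 35%, target 60%, 29 evaluable, success at 14 or more (SAP 3.1). At the futility look, 2 of 10 evaluable with 13 enrolled. A stop table with limits 2 of 10, 3 of 11, 3 of 12 and 4 of 13 (SAP 5.7.2).

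**2. The plan's own design, reproduced.** With X binomial(29, p):
- type I error = P(X ≥ 14 | 0.35) = 0.0978, within the stated 0.1;
- power = P(X ≥ 14 | 0.60) = 0.9290, within the stated 90% or more.

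**3. How the definitions treat four kinds of subject.** These are illustrations. The documents do not say that A, B or C occurred.

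| Subject | Week-12 status, SAP 5.7.1 event | Protocol 10.4.3 | SAP 4.2 | SAP 5.7.2 |
|---|---|---|---|---|
| A. Stops drug before Week 12; Week 6 and Week 12 scans clear; no later progression | success | in | out | out |
| B. As A, but progresses off treatment after Week 12 | success | in | out | in, shown as a progression |
| C. Dies before Week 12, one scan, no progression documented | failure | out | out | out |
| D. On drug and clear at Week 12, progresses later on drug | success | in | in | in, fits both groups |

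B separates SAP 4.2 from SAP 5.7.2. A and B separate SAP 4.2 from the protocol. C is an endpoint failure that none of the three sets admits.

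**4. Overlap.** If the 2 of 10 was counted under SAP 4.2, the other 10 − 2 = 8 progressed on treatment. If neither success progresses later, the display shows 2 and 8. If both do, it shows 2 and 8 + 2 = 10, which is 12 entries for 10 subjects. The Week-12 failure count cannot be read off either way.

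**5. The missing estimate.** The exact (Clopper-Pearson) 95% limits for x of n are the 0.025 quantile of Beta(x, n − x + 1) and the 0.975 quantile of Beta(x + 1, n − x).
- 2/10 = 20.0%, CI 2.5% to 55.6%.
- P(X ≤ 2 | n = 10, p = 0.60) = 0.0123.
- P(X ≤ 2 | n = 10, p = 0.35) = 0.2616.

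**6. All 13 enrolled at the look.** The Week-12 status of the other 13 − 10 = 3 is not given, so this is a range under an assumption.
- All 3 failures: 2/13 = 15.4%, CI 1.9% to 45.4%.
- All 3 successes: (2 + 3)/13 = 38.5%, CI 13.9% to 68.4%.

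The fourteenth subject is outside this range: "A fourteenth patient was enrolled, but the study was closed (due to futility) before week 12".

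**7. The stop table.** 2 of 10 meets the limit. With one added success, 3 of 11 still meets it. 4 of 12 and 5 of 13 would not, but nothing in the documents points to those counts.

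**The case against.** The case for leaving the SAP alone has real weight.

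- *Disclosure.* SAP Sections 4, 5, 5.7.2, 5.7.3 and 7 all say that efficacy reporting is limited and descriptive after the early stop. A reader might infer that the primary result is being hidden, but the documents do not support that.
- *The count is already given.* SAP 5.7.2 states 2 of 10. Within the SAP 4.2 set, being dosed 12 weeks without progression is close to the progression-free numerator. A reader might infer that a different endpoint has been substituted, which is too strong. What is lacking is the percentage, its interval, a titled table and an unambiguous denominator.
- *The protocol loses some of the same subjects.* Scans are six-weekly, so a subject who dies before Week 12 normally has at most one post-baseline scan. Such a subject fails Protocol 10.4.3 unless clinical progression was recorded. Some early stoppers would fail it too. SAP 4.2 is therefore not the sole cause of these exclusions.
- *Precedence.* Protocol 10.1 lets the SAP prevail. That permits a different definition, but not one described as the protocol's own.
- *Nothing more was promised.* Protocol 10.7 attaches its exact interval to best overall response, not to 12-week PFS. With at most 14 subjects and a declared stop, leaving out Kaplan-Meier output is a defensible choice.
- *Sparse off-treatment data.* Long-term follow-up is every 3 months (±1 month), may be by record review, and ends at new treatment. For an early stopper, the first contact will often fall after Week 12.

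These arguments limit the point. They do not reconcile SAP 4.2, SAP 5.7.2 and Protocol 10.4.3, and a plan without hypothesis testing can still report a number, a percentage and an interval.

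**Conclusion.** The point holds as a reporting gap and an inconsistency of definition, and should be corrected before the report is written. The endpoint in SAP 5.7.1 has no table, the two groups in SAP 5.7.2 can overlap, and the evaluable set differs between SAP 4.2, SAP 5.7.2 and Protocol 10.4.3 without an entry in SAP Section 7.

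On the SAP's 2 of 10, the rate is 20.0% with an interval that lies below 60% but does not exclude 35%. A reader might infer that the trial rules out the 60% target in all treated subjects. That is not supported: at 5 of 13 the upper limit is 68.4%. A reader might also infer that the futility stop was wrong. The documents do not support that either, since 2 of 10 meets the stop limit, as 3 of 11 would.

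Assumptions: 2 of 10 is a snapshot at the futility look, not a final count; all 13 enrolled were treated; and the intervals take n as fixed and ignore the unplanned stop. The documents do not say why 3 of the 13 were not evaluable. They may simply not have reached 12 weeks.

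**What to change.** 1. Use one wording for the evaluable set in SAP 4.2 and 5.7.2, with a single choice between progression on treatment and progression at any time.
2. In SAP Section 7, list how that wording differs from Protocol 10.4.3: the required Week-12 assessment, the 12 weeks of treatment, and the type and timing of progression. Remove the attribution to the protocol.
3. Add one descriptive table to SAP Section 9: number and percentage progression-free at Week 12 with exact 95% CI. Failure is progression, or death from any cause, up to and including the Week-12 assessment.
4. Give it for the evaluable set and, labelled supportive and post hoc, for all treated subjects. In the latter, show unknown Week-12 status (including the fourteenth subject if cut off by closure) as NE, with a worst-case and best-case range.
5. Keep dosing duration as an exposure summary, and label the efficacy output descriptive after an unplanned futility stop. A Kaplan-Meier summary is optional.

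Cost: a short text edit and minor programming for at most 14 subjects, with no change to trial conduct. The downsides are visibly wide intervals and possibly several NE subjects, because follow-up off treatment is sparse. The all-treated analysis is chosen after the result is known, hence its label.

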**5.7.3. Secondary Efficacy Endpoints**

Secondary efficacy endpoints were to include:

- Median PFS
- Best Overall Response (BOR)
- Overall Response Rate (ORR)
- Duration of Response (DOR)
- Time to Response (TTR)
- Overall Survival (OS)

BOR will be tabulated, and overall response will be recorded in listings, but otherwise, analyses of secondary efficacy endpoints will not be performed because this study was prematurely ended due to a lack of efficacy.

## 5.8. SAFETY

Data from all subjects that receive at least one dose of SPH4336 (Safety Population) will be included in the safety analyses.

### 5.8.1. Adverse Events

Treatment emergent adverse events (TEAEs) will be coded by System Organ Class and preferred term using MedDRA version 23.0 or higher. The investigator grades the severity/intensity of each AE with National Cancer Institute Common Terminology Criteria for Adverse Events (CTCAE) v5.0 and categorizes the relatedness of the AE to SPH4336.

Summaries that are displayed by system organ class and preferred terms will be ordered by descending incidence of system organ class and preferred term within each system organ class. Summaries of the following types will be presented:

- Overall Summary of Treatment-Emergent Adverse Events;
- Treatment-Emergent Adverse Events by System Organ Class and Preferred Term;
- Related Treatment-Emergent Adverse Events by CTCAE Grade, System Organ Class and Preferred Term;
- CTCAE Grade 3 or Higher Treatment-Emergent Adverse Events by System Organ Class and Preferred Term;
- Serious Treatment-Emergent Adverse Events by System Organ Class and Preferred Term;
- Treatment-Emergent Adverse Events Leading to Death by System Organ Class and Preferred Term;
- Treatment-Emergent Adverse Events Leading to Discontinuation of SPH4336 by System Organ Class and Preferred Term;

Summaries of AEs will include the number and percentages of subjects with each preferred term and SOC unless specified otherwise. Missing onset dates will be imputed as previously outlined in Section 3.3.5.1 as required to determine treatment-emergent events.

All adverse events reported will be listed for individual subjects showing both verbatim and preferred terms. All adverse events that occurred prior to the initiation of study drug or more than 28 days after last dose of study drug will be excluded from the tables, but will be included in the listings. No imputation for missing severity or relationship will be applied for listings.

### 5.8.2. Clinical Laboratory Assessments

Results from both local laboratories and the central laboratory used in this study are included in all data displays.

All descriptive summaries of laboratory results will be presented in Système International (SI) units, as suggested by the Center for Biologics Evaluation and Research and the Center for Drug Evaluation and Research *Position on Use of SI Units for Lab Tests* (Oct 2013). Descriptive

statistics of chemistry, hematology, and coagulation clinical laboratory results and their corresponding change from baseline will be presented at each visit where parameters were scheduled to be collected per the clinical study protocol.

Where applicable, hematology, chemistry and coagulation results for select parameters will be assigned a toxicity grade based on the U.S. Department of Health and Human Services Common Terminology Criteria for Adverse Events (CTCAE), version 5.0 (27 Nov 2017). If the quantitative criteria for grading are equivalent for two grades and the differentiation is described by clinical interventions, the clinical intervention component will not be considered and the highest CTCAE grade will be assigned. Similarly, death related to AE (i.e., Grade 5) cannot be determined with available laboratory-based data collection and, thus, will not be summarized as a category. Laboratory parameters that include multiple sets of criteria for each direction (e.g., separate criteria for potassium measures to assess hyperkalemia and hypokalemia) will be summarized separately to reflect each set of criteria.

Five-by-five contingency tables will be presented for lab tests where toxicity grading can be applied, to summarize the shift from the baseline grade to the worst post-baseline grade. Grades will be presented as none (Grade 0; i.e., measurements did not meet any CTCAE criteria for Grades 1 through 4), mild (Grade 1), moderate (Grade 2), severe (Grade 3), or life-threatening (Grade 4). Summary results will include the count and percentage of subjects within each shift category. Hematology, chemistry and coagulation parameters will be presented in data listings.

### **5.8.3. Prior and Concomitant Medications**

Prior and concomitant medications will be coded using the WHO Drug Dictionary (WHODD) Global B3 March 2022 or later. Medications entered on the eCRF will be mapped to Anatomic Therapeutic Chemical (ATC) drug class and drug name.

Concomitant medications will be summarized. The number and percentage of subjects receiving any medication will be summarized, as will the number and percentage receiving any medication by ATC drug class and generic drug name. Subjects reporting use of more than one medication at each level of summarization (any medication received, ATC class, and generic drug name) will be counted only once. ATC class terms will be displayed by descending order of incidence, as will generic drug names within each ATC class.

All medications will be listed.

### **5.8.1. Concomitant Procedures**

Concomitant procedures will be coded using MedDRA Version 22.0 or later. Concomitant procedures will be summarized. The number and percentage of subjects receiving any procedures will be summarized, as will the number and percentage receiving any procedures by system organ class (SOC) and preferred term. Subjects reporting more than one procedure at each level of summarization (any procedure, SOC, and preferred term) will be counted only once. All procedures will be listed.

#### **5.8.1.      Electrocardiogram (ECG)**

Descriptive statistics of heart rate/pulse (beats/min), RR interval (msec), PR interval (msec), QRS interval (msec), QT interval (msec) and QTcF (msec) interval and changes from baseline will be summarized, as well shift tables for overall interpretation. ECG parameters will be presented in data listings.

#### **5.8.2.      Vital Signs**

Descriptive statistics for vital signs including heart rate (beats per minute), respiratory rate (breaths per minute), systolic blood pressure (mmHg), diastolic blood pressure (mmHg), and temperature (Fahrenheit) values and changes from baseline will be summarized.

Vital signs parameters will be presented in data listings.

#### **5.8.1.      ECOG**

The number and percentage of subjects with each ECOG performance status (0, 1, 2, 3, 4, 5) will be summarized categorically. Change from baseline for each post-baseline visit will also be summarized.

A listing of ECOG performance status results will be presented.

### **6.            PROTOCOL DEVIATIONS**

Subjects with protocol deviations will be presented in data listings.

### **7.            CHANGES IN THE PLANNED ANALYSES**

The study ended prematurely because of a lack of efficacy in study patients. Therefore, a formal analysis of efficacy will not be performed. Biomarker analysis was also not performed.

No other changes in the planned analysis are anticipated. Should any deviations from the analyses specified in the authorized statistical analysis plan arise, such deviations will be documented in the final clinical study report.

## 9. **PROPOSED TABLES, LISTINGS, AND FIGURES**

Number	Title	Population
Tables		
14.1.1	Subject Disposition	Safety
14.1.2	Demographic Characteristics	Safety
14.1.3	Baseline Characteristics and Cancer History	Safety
14.1.4	Medical History	Safety
14.1.5	Prior Therapies and Surgery	Safety
14.1.6	Study Drug Exposure and Compliance	Safety
14.2.1	Best Overall Response	Efficacy
14.3.1.1	Overall Summary of Treatment-Emergent Adverse Events	Safety
14.3.1.2	Treatment-Emergent Adverse Events by System Organ Class and Preferred Term	Safety
14.3.1.3	Related Treatment-Emergent Adverse Events by CTCAE Grade, System Organ Class and Preferred Term	Safety
14.3.1.4	CTCAE Grade 3 or Higher Treatment-Emergent Adverse Events by System Organ Class and Preferred Term	Safety
14.3.1.5	Serious Treatment-Emergent Adverse Events by System Organ Class and Preferred Term	Safety
14.3.1.6	Treatment-Emergent Adverse Events Leading to Death by System Organ Class and Preferred Term	Safety
14.3.1.7	Treatment-Emergent Adverse Events Leading to Discontinuation of SPH4336 by System Organ Class and Preferred Term	Safety
14.3.2.1	Listing of Deaths	Safety
14.3.2.2	Listing of Serious Adverse Events	Safety
14.3.2.3	Listing of Grade 3 or Higher Adverse Events	Safety
14.3.2.4	Listing of Adverse Events Leading to Discontinuation of SPH4336	Safety
14.3.3.1	Hematology Results and Changes from Baseline	Safety
14.3.3.2	Shift in Hematology Laboratory Values in CTCAE Toxicity Grade to the Worst Abnormal Value	Safety
14.3.3.3	Chemistry Results and Changes from Baseline	Safety
14.3.3.4	Shift in Chemistry Laboratory Values in CTCAE Toxicity Grade to the Worst Abnormal Value	Safety
14.3.3.5	Coagulation Results and Changes from Baseline	Safety
14.3.3.6	Shift in Coagulation Laboratory Values in CTCAE Toxicity Grade to the Worst Abnormal Value	Safety

14.3.4.1	Concomitant Medications	Safety
14.3.4.2	Concomitant Procedures	Safety
14.3.5.1	Vital Signs Results and Changes from Baseline	Safety
14.3.5.2	12-Lead Electrocardiogram - Univariate Summary by Parameter and Visit	Safety
14.3.5.3	12-Lead Electrocardiogram Interpretation -- Shift from Baseline to Worst Post-Baseline Value	Safety
14.3.6	Summary of ECOG Performance Status	Safety

